7.4 Obinutuzumab

7.4.1 Description and Mode of Action

Obinutuzumab is a humanized and glycoengineered type II anti-CD20 monoclonal antibody of the IgG1 subclass. It recognizes a specific epitope of the CD20 molecule found on B-cells. The molecular mass of the antibody is approximately 150 kDa. The enhanced affinity of obinutuzumab for the low and high affinity Fc γ RIIIa by glycoengineering translated into a significantly enhanced (5-100-fold) potency in ADCC assays in comparison to rituximab and ofatumumab

7.4.2 Formulation, Packaging, and Storage

Obinutuzumab is provided as a single 1000 mg dose liquid concentrate with a strength of 25 mg/mL. It is supplied in 50 mL glass vials containing 40 mL of the 25 mg/mL liquid concentrate. In addition to the antibody, the liquid also contains histidine/histidine-HCl, trehalose, poloxamer 188 and water for injection. Water meets the specified limits for "Water for Injections" according to Ph. Eur. monograph and "Water for Injection" according to USP monograph. The recommended storage conditions for obinutuzumab drug product are between 2°C and 8°C, protected from light. For further instructions as well as information on in-use stability, see the packaging label.

7.4.3 Clinical Use

Cycle 1: The recommended dosage of obinutuzumab is 1000 mg administered over Day 1-and Day 2, and on Day 8 and Day 15 of the first 28-day treatment cycle. Two infusion bags should be prepared for the first dose: 100 mg for the first infusion and 900 mg for the second infusion.

Cycles 2-6: The recommended dosage of obinutuzumab is 1000 mg administered on Day 1 for each 28 day treatment cycle.

- Cycle 1 Day 1, 100 mg: Administer at 25 mg/hr over 4 hours. Do not increase the infusion rate.
- Cycle 1 Day 2, 900 mg: If no IRR occurred during the previous infusion, administer at 50 mg/hr. The rate of the infusion can be escalated in increments of 50 mg/hr every 30 minutes to a maximum rate of 400 mg/hr. If the patient experienced an IRR during the previous infusion, start administration at 25 mg/hr. The rate of infusion can be escalated in increments of up to 50 mg/hr every 30 minutes to a maximum rate of 400 mg/hr.

- Cycle 1 Day 8 1000 mg, Day 15 1000 mg: If no IRR occurred during the previous infusion where the final infusion rate was ≥ 100 mg/hr, infusions can be started at a rate of 100 mg/hr and increased by 100 mg/hr increments every 30 minutes to a maximum of 400 mg/hr. If the patient experienced an IRR during the previous infusion administer at 50 mg/hr. The rate of the infusion can be escalated in increments of 50mg/hr every 30 minutes to a maximum rate of 400 mg/hr.
- Cycles 2-6 Day 1 1000 mg: : If no IRR occurred during the previous infusion where the final infusion rate was ≥ 100 mg/hr, infusions can be started at a rate of 100 mg/hr and increased by 100 mg/hr increments every 30 minutes to a maximum of 400 mg/hr. If the patient experienced an IRR during the previous infusion administer at 50 mg/hr. The rate of the infusion can be escalated in increments of 50mg/hr every 30 minutes to a maximum rate of 400 mg/hr.

7.4.4 Nursing Implications

Premedications are used to reduce the risk of IRRs. For the first infusion of obinutuzumab, corticosteroid premedication is mandatory. Premedication for subsequent infusions and other premedication should be administered as described below. Hypotension, as a symptom of IRR, may occur during obinutuzumab intravenous infusions. Therefore, withholding of antihypertensive treatments should be considered for 12 hours prior to and throughout each obinutuzumab infusion and for the first hour after administration.

- Cycle 1: All patients
 - Intravenous corticosteroid (e.g. 100 mg prednisone, or 20 mg dexamethasone, or 80 mg methylprednisolone) at least 1 hour prior to obinutuzumab infusion.
 - Oral analgesic/anti-pyretic (e.g. 1000 mg acetaminophen/paracetamol) and anti-histaminic drug (e.g. 50 mg diphenhydramine) at least 30 minutes before Obinutuzumab infusion.
- All subsequent infusions:
 - Patients with no IRR during the previous infusion
 - Oral analgesic/anti-pyretic (e.g. 1000 mg acetaminophen/paracetamol) at least 30 minutes before Obinutuzumab infusion.
 - Patients with an IRR (Grade 1 or 2) with the previous infusion
 - Oral analgesic/anti-pyretic (e.g. 1000 mg acetaminophen/paracetamol) and anti-histaminic drug (e.g. 50 mg diphenhydramine) at least 30 minutes before Obinutuzumab infusion.
 - Patients with a Grade 3 IRR with the previous infusion OR Patients with lymphocyte counts $>25 \times 10^9/L$ prior to next treatment
 - Intravenous corticosteroid (e.g. 100 mg prednisone, or 20 mg dexamethasone, or 80 mg methylprednisolone) at least 1 hour prior to obinutuzumab infusion.
 - Oral analgesic/anti-pyretic (e.g. 1000 mg acetaminophen/paracetamol) and anti-histaminic drug (e.g. 50 mg diphenhydramine) at least 30 minutes before obinutuzumab

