5.3.4 Obinutuzumab Administration

Each dose of obinutuzumab is 1000 mg, administered intravenously, with the exception of the first infusions in Cycle 1, which are administered on Day 1 (100 mg) and Day 2 (900 mg) (Table 4).

Table 4 Obinutuzumab Dosing Schedule

Cycle and Day of Administration		Dose of Obinutuzumab	Rate of Infusion (in the Absence of Infusion Reactions/ Hypersensitivity during Previous Infusions)
Cycle 1	Day 1	100 mg	Administer at 25 mg/hour over 4 hours. Do not increase the infusion rate.
	Day 2	900 mg	Administer at 50 mg/hour if no infusion reaction occurred during the previous infusion. The rate of the infusion can be escalated in increments of 50 mg/hour every 30 minutes to a maximum rate of 400 mg/hour.
	Day 8	1000 mg	If no infusion reaction occurred during the previous infusion and the final infusion rate was 100 mg/hr or faster, infusions can be started at a rate of 100 mg/hour and increased by 100 mg/hour increments every 30 minutes to a maximum of 400 mg/hour.
	Day 15	1000 mg	
Cycles 2–6, Subsequent cycles	Day 1	1000 mg	If no infusion reaction occurred during the previous infusion and the final infusion rate was 100 mg/hr or faster, infusions can be started at a rate of 100 mg/hour and increased by 100 mg/hour increments every 30 minutes to a maximum of 400 mg/hour.
Additional cycles	Every 2 months, starting cycle 8	1000 mg	

If a planned dose of obinutuzumab is missed, administer the missed dose as soon as possible and adjust dosing schedule to maintain the time interval between doses. If appropriate, patients who do not complete the Day 1 Cycle 1 dose may proceed to the Day 2 Cycle 1 dose.

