Obinutuzumab should be administered as a slow IV infusion through a dedicated line. IV infusion pumps (e.g., Braun Infusomat® Space) should be used to control the infusion rate of obinutuzumab. Do not administer as an IV push or bolus. After the end of the first infusion, the IV line or central venous catheter should remain in place for \geq 2 hours in order to be able to administer IV drugs if necessary. If no adverse events occur after 2 hours, the IV line may be removed or the central venous catheter may be de-accessed. For subsequent infusions, access (either IV line or central venous catheter) should remain in place for at least 30 minutes from the end of infusion, and if no adverse events occur after 30 minutes, the IV access may be removed. During the maintenance phase, the IV access may be removed at the end of infusion if no adverse events occurred during the infusion.

All obinutuzumab infusions should be administered after premedication with oral acetaminophen (e.g., 650–1000 mg) and an antihistamine, such as diphenhydramine (50–100 mg), 30–60 minutes prior to starting each infusion (unless contraindicated). The use of prophylactic corticosteroids (e.g., prednisolone 100 mg IV or equivalent) is recommended prior to the first dose of obinutuzumab in Cycle 1. Corticosteroids may also be considered for subsequent infusions in

patients who are thought to be at high risk for IRRs, if deemed appropriate by the investigator. In patients who do not experience a Grade ≥ 2 IRR with their previous infusion (i.e., do not receive medication to treat IRR symptoms and do not experience infusion interruption), premedication for subsequent infusions may be omitted at the investigator's discretion.

Patients who are considered to have a high tumor burden and who are considered to be at risk for tumor lysis syndrome (TLS) by the investigator should also receive TLS prophylaxis prior to the initiation of treatment. These patients should be well hydrated. Starting 1–2 days before the first dose of obinutuzumab, it is desirable to maintain a fluid intake of approximately > 3 L/day. These patients should continue to receive repeated prophylaxis with allopurinol and adequate hydration prior to each subsequent infusion, if deemed appropriate by the investigator.

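### Steroid before the first obinutuzumab infusion is mandatory in Section 7.4.4 but only recommended in 5.3.4, and the 5.3.4 omission clause is ambiguous for the 900 mg Day 2 infusion

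*Combined protocol and SAP*

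**What the plan says.** **Section 7.4.4 (Nursing Implications).** The rule for the first infusion is strict: "For the first infusion of obinutuzumab, corticosteroid premedication is mandatory". Under the label "Cycle 1: All patients" the section lists three drugs: an IV corticosteroid at least 1 hour before, and an oral analgesic and an antihistamine at least 30 minutes before. A second list, for subsequent infusions, steps down according to the reaction to the previous infusion. Its lowest step, for patients with no reaction, still includes an oral analgesic.

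**Section 5.3.4 (Obinutuzumab Administration).** The default is two drugs, an analgesic and an antihistamine, unless contraindicated: "All obinutuzumab infusions should be administered after premedication with oral acetaminophen". A prophylactic corticosteroid "is recommended prior to the first dose of obinutuzumab in Cycle 1". After that, "Corticosteroids may also be considered for subsequent infusions in" patients thought to be at high risk of infusion-related reactions (IRRs). For patients with no Grade 2 or higher IRR at the previous infusion, explained as those who "do not receive medication to treat IRR symptoms and do not experience infusion interruption", the section says that "premedication for subsequent infusions may be omitted" at the investigator's discretion. No exception is made for Cycle 1.

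**Dosing (Section 5.3.4 Table 4 and Section 7.4.3).** The first 1000 mg is split into 100 mg on Day 1 and 900 mg on Day 2.

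**The concern.** The two sections give different instructions for the same infusion. A site that writes its orders from the administration section could treat the first-infusion steroid as optional, although the protocol requires it elsewhere. The same site might also be unsure whether premedication may be dropped on Day 2 after a quiet Day 1.

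Section 7.4.5 says that IRRs occurred mostly during the first 1000 mg and fell substantially afterwards, and that severe and life-threatening reactions have been reported. The first 1000 mg is Days 1 and 2, so the unclear instruction falls in the period where the protocol itself places most of the risk.

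**Working it through.** There is no statistical figure to reproduce. The check sets the texts side by side, with simple dose arithmetic.

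**Step 1. Status of the steroid at the first infusion.**
- Section 7.4.4: mandatory.
- Section 5.3.4: recommended.
- Precedence: neither section defers to the other. Section 5.3.4 refers to the package insert and the Investigator's Brochure for further information, which does not settle the conflict within the protocol.

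This mismatch does not depend on how *first dose* or *subsequent infusions* is read.

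**Step 2. Does the omission clause cover Day 2?** The clause applies to *subsequent infusions*, so the question is whether Day 2 is one.
- Pointing to no: the opening sentence of 5.3.4 groups Day 1 and Day 2 together as the first infusions in Cycle 1. The infusion-rate paragraph in 5.3.4 also uses *subsequent infusions*, for infusions that start at 100 mg/hr. Table 4 starts Day 2 at 50 mg/hr, so that use cannot include Day 2.
- Pointing to yes: Section 7.4.3 calls the 100 mg bag the first infusion and the 900 mg bag the second. The Day 2 row of Table 4 refers to the *previous infusion*, which there can only be Day 1. The clause itself has no Cycle 1 exception.

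Both readings are open. The first is the more natural one within 5.3.4.

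**Step 3. What 7.4.4 asks for on Day 2.**
- Read by cycle, Day 2 falls under the three-drug list.
- Read strictly, with everything after the first infusion counted as subsequent, a patient without a reaction still receives an analgesic.
- If the 5.3.4 omission clause does apply to Day 2, it permits no premedication at all, which is less than 7.4.4 gives on either reading.

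**Step 4. Condition attached to the clause.** For infusion rate, 5.3.4 counts an infusion as well tolerated only if the final rate was at least 100 mg/hr. The Day 1 instruction is "Administer at 25 mg/hour over 4 hours", with no rate increase allowed, so Day 1 cannot meet that condition. The premedication clause carries no rate condition.

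**Step 5. Dose arithmetic (Table 4).**
- Day 1: 25 mg/hr × 4 h = 100 mg; 100/1000 = 10% of the first 1000 mg.
- Day 2: 900/1000 = 90%.
- Day 2 starting rate relative to Day 1: 50/25 = 2 times; maximum rate: 400/25 = 16 times.

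**Step 6. Exposure.** The ALO cohort is planned at 10 patients with one Day 2 infusion each: 10 × 1 = 10. This is an upper bound. Reaching it would require the literal reading in Step 2, no Grade 2 or higher IRR on Day 1 in any of the 10, and a decision to omit in every case.

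**The case against.** The strongest reply has three parts.

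First, on Day 2, the opening of 5.3.4 treats Days 1 and 2 as one group of first infusions, so the omission clause most naturally starts after Day 2. By the same logic, *first dose* spans both days, since 7.4.3 prepares two bags for it, and the steroid recommendation then reaches Day 2. This largely stands. A reader might infer that the protocol authorises giving the 900 mg infusion without premedication. The documents do not support so firm a statement; they support only that the wording leaves the point open. Extending the recommendation to Day 2 would also not make it a requirement.

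Second, the sentence in 7.4.4 that makes the steroid mandatory concerns the first infusion. If Day 2 is called the second infusion, only the Cycle 1 list covers it. This stands too, and it is why an explicit Day 2 requirement is presented as a proposal.

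Third, a site that follows 7.4.4 breaches neither section, and omission always needs an investigator's decision. Both are true, and they limit the consequence. They do not remove the conflict, because a site that follows 5.3.4 can give less than 7.4.4 requires at the first infusion.

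**Conclusion.** The point holds as an internal inconsistency in a patient-safety instruction. The mismatch between mandatory and recommended is certain on the current text. The Day 2 question is an ambiguity and should be described as one.

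The reach is small: one cohort of 10 patients, with 10 Day 2 infusions as a ceiling and not an expected count.

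A reader might go on to infer that more IRRs would follow, or that the safety run-in or the feasibility decision would be distorted. The documents give no basis for this. The reduction in IRRs described in Section 7.4.5 was seen in CLL patients given a bundle of measures, so no effect of steroid alone in this population can be derived. No effect on the run-in, the feasibility criteria, the sample size or the analysis is claimed.

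The text should be corrected because the change is cheap and concerns the period of highest stated reaction risk.

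**What to change.** **Section 5.3.4.**
- Replace the steroid sentence with: *IV corticosteroid premedication is mandatory before the first dose of obinutuzumab (Cycle 1 Day 1 and Day 2 infusions), with analgesic and antihistamine, per Section 7.4.4.* The contraindication exception in the default sentence can stay.
- Add to the omission clause: *This does not apply to the Cycle 1 Day 1 or Day 2 infusions; for later infusions follow Section 7.4.4.* Since 7.4.4 keeps at least an analgesic at every infusion, the sponsor should make clear in the same edit that omission goes no further than 7.4.4 allows.

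**Section 7.4.4.**
- Change the scope of the mandatory sentence from the first infusion to *the first 1000 mg (Cycle 1 Days 1 and 2)*.
- Head the second list *All subsequent infusions (after Cycle 1)*. Days 8 and 15 then stay under the Cycle 1 list, as its label now reads, unless the sponsor specifies otherwise.

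Making the steroid explicitly mandatory on Day 2 is this review's proposal. It rests on the Cycle 1 list in 7.4.4 and the timing of IRRs in 7.4.5.

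**Cost.** Wording in two sections. Design, sample size and analysis are unchanged.

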7.4.5 Warnings and Precautions

Infusion Related Reactions (IRR)

The most frequently observed adverse drug reactions (ADRs) in patients receiving obinutuzumab were IRRs which occurred predominantly during infusion of the first 1000 mg. In patients with CLL who received the combined measures for prevention of IRRs (adequate corticosteroid, oral analgesic/anti-histamine, omission of antihypertensive medication), a decreased incidence of IRRs of all grades was observed. The incidence and severity of infusion-related symptoms decreased substantially after the first 1000 mg was infused, with most patients having no IRRs during subsequent administrations of obinutuzumab. In the majority of patients, irrespective of indication, IRRs were mild to moderate and could be managed by the slowing or temporary halting of the first infusion, but severe and life-threatening IRRs requiring symptomatic treatment have also been reported. IRRs may be clinically indistinguishable from IgE-mediated allergic reactions (e.g., anaphylaxis). Patients with a high tumor burden and/or high circulating lymphocyte count in CLL [$> 25 \times 10^9/L$] may be at increased risk of severe IRR. Patients should not receive further obinutuzumab infusions if they experience:

- acute life-threatening respiratory symptoms,
- a Grade 4 (i.e., life-threatening) IRR or,
- a second occurrence of a Grade 3 (prolonged/recurrent) IRR (after resuming the first infusion or during a subsequent infusion).

Patients who have pre-existing cardiac or pulmonary conditions should be monitored carefully throughout the infusion and the post-infusion period. Hypotension may occur during obinutuzumab intravenous infusions. Therefore, withholding of antihypertensive treatments should be considered for 12 hours prior to and throughout each obinutuzumab infusion and for the first hour after administration. Patients at acute risk of hypertensive crisis should be evaluated for the benefits and risks of withholding their anti-hypertensive medication.

Hypersensitivity Reactions

Hypersensitivity reactions with immediate (e.g., anaphylaxis) and delayed onset (e.g. serum sickness), have been reported in patients treated with obinutuzumab. If a hypersensitivity reaction is suspected during or after an infusion (e.g., symptoms typically occurring after previous exposure and very rarely with the first infusion), the infusion should be stopped and treatment permanently discontinued. Patients with known hypersensitivity to obinutuzumab must not be treated. Hypersensitivity may be clinically difficult to distinguish from infusion related reactions.

Tumor Lysis Syndrome

TLS, including fatal TLS, has been reported with obinutuzumab. Patients who are considered to be at risk of TLS [e.g., patients with a high tumor burden or a high circulating lymphocyte count ($> 25 \times 10^9/L$)] and/or renal impairment (CrCl < 70 mL/min)] should receive prophylaxis. Prophylaxis should consist of adequate hydration and administration of uricostatics (e.g., allopurinol), or a suitable alternative such as a urate oxidate (e.g., rasburicase), prior to the infusion of obinutuzumab. All patients considered at risk should be carefully monitored during the initial days of treatment with a special focus on renal function, potassium, and uric acid values. Any additional guidelines according to standard practice should be followed. For treatment of TLS,

correct electrolyte abnormalities, monitor renal function and fluid balance, and administer supportive care, including dialysis as indicated.

Neutropenia

Severe and life-threatening neutropenia including febrile neutropenia has been reported during treatment with obinutuzumab. Patients who experience neutropenia should be closely monitored with regular laboratory tests until resolution. If treatment is necessary, it should be administered in accordance with local guidelines and administration of granulocyte colony-stimulating factors (G-CSF) should be considered. Any signs of concomitant infection should be treated as appropriate. Late onset neutropenia (occurring 28 days after the EoT) or prolonged neutropenia (lasting more than 28 days after treatment has been completed/ stopped) may occur.

Thrombocytopenia

Severe and life-threatening thrombocytopenia including acute thrombocytopenia (occurring within 24 hours after the infusion) has been observed during treatment with obinutuzumab. Fatal hemorrhagic events have also been reported in Cycle 1 in patients with CLL treated with obinutuzumab. A clear relationship between thrombocytopenia and hemorrhagic events has not been established. Patients should be closely monitored for thrombocytopenia, especially during the first cycle; regular laboratory tests should be performed until the event resolves, and dose delays should be considered in case of severe or life-threatening thrombocytopenia. Transfusion of blood products (i.e., platelet transfusion) according to institutional practice is at the discretion of the treating physician. Use of any concomitant therapies, which could possibly worsen thrombocytopenia related events such as platelet inhibitors and anticoagulants, should also be taken into consideration, especially during the first cycle.

Prolonged B-cell Depletion

B-cell depletion is defined as a CD19+ B-cell count of $< 0.07 \times 10^9$ cells/L by flow cytometry (FACS) in whole blood and can only occur after at least one dose of study drug has been administered. B-cell recovery is defined as when B cells are no longer depleted (i.e., $\geq 0.07 \times 10^9$ cells/L) and can only occur after the patient has completed study treatment. Prolonged B-cell depletion is defined as the absence of B-cell recovery 12 months after the end of treatment. In a large proportion of patients with relapsed NHL, CD19+ B-cell counts were markedly low at baseline, possibly as a result of previously administered therapy with an anti-CD20 antibody or other treatments. Treatment with obinutuzumab resulted in a further decrease in the number of CD19+ B cells. This is consistent with the anticipated pharmacodynamic effect of obinutuzumab, which is primarily aimed at the depletion of B cells. Follow-up data are sparse and determining the actual timepoint at which recovery occurs is difficult. Prolonged B-cell depletion may be related to the risk of progressive multifocal leukoencephalopathy (PML) and HBV, which are described and assessed separately.

Worsening of Pre-existing Cardiac Conditions

In patients with underlying cardiac disease, arrhythmias (such as atrial fibrillation and tachyarrhythmia), angina pectoris, acute coronary syndrome, myocardial infarction and heart failure have occurred when treated with obinutuzumab. These events may occur as part of an IRR

and can be fatal. Therefore, patients with a history of cardiac disease should be monitored closely. In addition, these patients should be hydrated with caution in order to prevent a potential fluid overload.

Infections

Obinutuzumab should not be administered in the presence of an active infection and caution should be exercised when considering the use of obinutuzumab in patients with a history of recurring or chronic infections. Serious, bacterial, fungal, and new or reactivated viral infections can occur during and following the completion of obinutuzumab therapy. Fatal infections have been reported. In the FL studies, a high incidence of infections was observed in all phases of the studies, including follow-up, with the highest incidence seen in maintenance. During the follow-up phase, grade 3–5 infections are observed more in patients who received obinutuzumab plus benda in the induction phase.

Hepatitis B Reactivation

HBV reactivation, in some cases resulting in fulminant hepatitis, hepatic failure and death, can occur in patients treated with anti-CD20 antibodies including Obinutuzumab. HBV screening should be performed in all patients before initiation of treatment with obinutuzumab. At minimum this should include HBsAg-status and HBcAb-status. These can be complemented with other appropriate markers as per local guidelines. Patients with active Hepatitis B disease should not be treated with obinutuzumab. Patients with positive hepatitis B serology should consult liver disease experts before start of treatment and should be monitored and managed following local medical standards to prevent hepatitis reactivation. Please refer to respective protocols for detailed guidance on this subject.

Progressive Multifocal Leukoencephalopathy

PML has been reported in patients treated with obinutuzumab. The diagnosis of PML should be considered in any patient presenting with new-onset or changes to preexisting neurologic manifestations. The symptoms of PML are nonspecific and can vary depending on the affected region of the brain. Motor symptoms with corticospinal tract findings (e.g., muscular weakness, paralysis, and sensory disturbances), sensory abnormalities, cerebellar symptoms, and visual field defects are common. Some signs/symptoms regarded as “cortical” (e.g., aphasia or visual-spatial disorientation) may occur. Evaluation of PML includes, but is not limited to, consultation with a neurologist, brain MRI, and lumbar puncture (cerebrospinal fluid testing for JCV DNA). Therapy with obinutuzumab should be withheld during the investigation of potential PML and permanently discontinued in case of confirmed PML. Discontinuation or reduction of any concomitant chemotherapy or immunosuppressive therapy should also be considered. The patient should be referred to a neurologist for the evaluation and treatment of PML.

Immunization

The safety of immunization with live or attenuated viral vaccines, following obinutuzumab therapy has not been studied and vaccination with live virus vaccines is not recommended during treatment and until B-cell recovery.

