If a patient's previous infusion of obinutuzumab is well tolerated (defined by the absence of a \geq Grade 2 IRR during a final infusion rate of ≥ 100 mg/hr), subsequent infusions will be administered at an initial rate of 100 mg/hr and increased by 100-mg/hr increments at 30-minute intervals, as tolerated, to a maximum rate of 400 mg/hr. If a hypersensitivity reaction or an IRR develops, the infusion should be temporarily interrupted or slowed down and concomitant medication may be administered if deemed appropriate by the investigator. Upon resolution of symptoms, the infusion will resume at one-half the previous rate (the rate being used at the time that the hypersensitivity or IRR developed) and infusion rate escalation may resume at the increments and intervals described. If the previous infusion rate was not well tolerated, as defined, instructions for the first infusion rate will be used. For more information, please see the package insert and the Obinutuzumab Investigator's Brochure.

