6.6 Obinutuzumab

There will be no dose modifications of obinutuzumab. Treatment with obinutuzumab should be delayed for Grade 4 hematologic toxicity or clinically significant Grade ≥ 3 non-hematologic toxicity experienced at the time of scheduled dosing.

For hematologic toxicities, patients who experience Grade 4 toxicities should have their doses of obinutuzumab delayed for monitoring of resolution or improvement of toxicity. Dosing may resume upon the resolution of hematologic toxicity to Grade ≤ 3 or baseline status.

For non-hematologic toxicities, dosing may resume only upon resolution to Grade ≤ 2 or baseline. In addition, resumption of dosing without complete resolution of toxicity may be considered only upon careful weighing of the benefits and risks to the patient and agreement between the investigator and the Sponsor-investigator.

For management of symptomatic AEs (including IRRs), see below.

- **Grade 4 (life threatening):** Stop infusion and permanently discontinue therapy.
- **Grade 3 (severe):** Temporarily interrupt infusion and treat symptoms. Upon resolution of symptoms, restart infusion at no more than half the previous rate (the rate being used at the time that the IRR occurred). If patient does not experience any further IRR symptoms, infusion rate escalation may resume at the increments and intervals as appropriate for the treatment dose. If the patient experiences a second occurrence of a Grade 3 IRR, stop infusion and permanently discontinue therapy.
- **Grade 1&2 (mild and moderate):** Reduce infusion rate and treat symptoms. Upon resolution of symptoms, continue infusion. If patient does not experience any IRR symptoms, infusion rate escalation may resume at the increments and intervals as appropriate for the treatment dose.

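### Obinutuzumab (ALO cohort): for a suspected, non-life-threatening hypersensitivity reaction during an infusion, Section 5.3.4 resumes at half rate and Section 7.4.5 permanently discontinues

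*Combined protocol and SAP*

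**What the plan says.** Three sections bear on a reaction during an obinutuzumab infusion.

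- **Section 5.3.4 (administration).** "If a hypersensitivity reaction or an IRR develops, the infusion should be temporarily interrupted or slowed down". After symptoms resolve, "the infusion will resume at one-half the previous rate (the rate being used at the time that the hypersensitivity or IRR developed"), and rate escalation may start again. Hypersensitivity is named in both sentences, and no grade limit is given.
- **Section 6.6 (dose modification).** The graded rules are introduced by "For management of symptomatic AEs (including IRRs), see below". For Grade 4 the order is "Stop infusion and permanently discontinue therapy". For a first Grade 3 event it is "Temporarily interrupt infusion and treat symptoms. Upon resolution of symptoms, restart infusion at no more than half the previous rate". Grade 1 and 2 events are handled by slowing the infusion, treating symptoms and continuing. A second Grade 3 IRR ends the drug. Hypersensitivity is not mentioned.
- **Section 7.4.5 (warnings, Hypersensitivity Reactions).** If hypersensitivity is suspected during or after an infusion, "the infusion should be stopped and treatment permanently discontinued". No grade limit is given. The section adds: "Patients with known hypersensitivity to obinutuzumab must not be treated". It also says that these reactions typically follow an earlier exposure and are hard to tell from IRRs.

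**The concern.** Staff facing a suspected hypersensitivity reaction cannot both restart the infusion and end the drug for good. Section 5.3.4 is the section they would have open at the bedside. Followed exactly, it re-infuses a patient for whom Section 7.4.5 has already ended obinutuzumab.

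The stake is patient safety and uniform conduct across sites. Section 7.4.5 gives anaphylaxis as an example of such a reaction, and Section 3.3 excludes patients with known hypersensitivity to any study drug. Two sites could handle the same reaction in opposite ways, and each would depart from one section of the protocol. Because the protocol itself says the two kinds of reaction are difficult to separate, the written rule has to say what happens once hypersensitivity is suspected.

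**Working it through.** This is a comparison of texts. The plan states no figure on this point, so there is none to reproduce.

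**Step 1. Set the instructions side by side for one event: suspected hypersensitivity during an obinutuzumab infusion.**

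| Situation | 5.3.4 | 6.6 | 7.4.5 |
|---|---|---|---|
| Grade 1–2 | Interrupt or slow, then half rate | Slow, treat, continue | Stop for good |
| First Grade 3 | Interrupt or slow, then half rate | Interrupt, restart at half rate or less | Stop for good |
| Second Grade 3 IRR | No exception stated | Stop for good | Stop for good |
| Grade 4 or life-threatening | No exception stated | Stop for good | Stop for good |
| Onset after the infusion has ended | No infusion to resume | No infusion to restart | Stop for good |

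The first two rows are the unresolved conflict. In the third and fourth rows, 6.6 and 7.4.5 agree on permanent discontinuation. In the last row, the half-rate rule has nothing to act on.

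**Step 2. Look for a reading that reconciles them.**

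- *Could 5.3.4 mean IRRs only?* No. It lists hypersensitivity separately from IRR, twice. It also provides for the next infusion when the previous one was not well tolerated, so it expects treatment to go on.
- *Could 7.4.5 be background only?* No. Its IRR paragraph holds operative stopping rules (Grade 4, second Grade 3), and 6.6 repeats them. The hypersensitivity rule in the same section was not carried across.
- *Does 6.6 decide?* No. It has no hypersensitivity exception.
- *Is there a precedence clause?* None was found. The reference in 5.3.4 to the package insert and Investigator's Brochure is for further information only.

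**Step 3. Count the occasions.** Inputs are Table 4 in Section 5.3.4, where later doses are given "Every 2 months, starting cycle 8", and the 10 ALO patients in Section 11.2.

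- Cycle 1: Days 1, 2, 8 and 15 = 4 infusions.
- Cycles 2 to 6, Day 1 = 5 infusions.
- Cycles 8, 10 and 12 = 3 infusions.
- Per patient in induction: 4 + 5 + 3 = 12. For the cohort: 12 × 10 = 120.
- After a previous exposure: 12 − 1 = 11 per patient, or 110 for the cohort. If Days 1 and 2 count as one split first dose: 12 − 2 = 10 per patient, or 100 for the cohort.

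These are occasions on which the conflict could arise, not expected events. Maintenance infusions would add to them.

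**Step 4. Chance that at least one patient meets the conflict.** The documents give no hypersensitivity rate, so the risk p is an assumption. It is the per-patient risk of the narrow event only: suspected, Grade 1 to 3, during an infusion. With 10 independent patients, the chance is 1 − (1 − p)^10.

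- p = 1%: 1 − 0.99^10 = 0.0956, or 9.6%.
- p = 2%: 1 − 0.98^10 = 0.1829, or 18.3%.
- p = 5%: 1 − 0.95^10 = 0.4013, or 40.1%.

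**The case against.** The strongest case on the other side accepts the clash between 5.3.4 and 7.4.5 and argues that its reach is small.

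- **Staff are not bound to re-infuse.** Section 6.8 lets the investigator discontinue anyone for whom further therapy is no longer safe. That is true, but it only permits stopping. It does not withdraw the instruction in 5.3.4 to resume.
- **The ban on treatment applies to known hypersensitivity, not suspected.** The distinction is correct. It makes no practical difference here, because the rule for suspected reactions already ends the drug permanently.
- **Section 6.6 is a weak second conflict.** This stands in part. Section 6.6 never names hypersensitivity, and its Grade 3 text speaks of IRRs, so it can be read as a general rule beside a specific one in 7.4.5. The direct contradiction is between 5.3.4 and 7.4.5.
- **The numbers are soft.** This also stands. The count after previous exposure may be 10 rather than 11 per patient, and nothing in the documents supports the 1% to 5% risk. The finding does not depend on either.
- **Letting 7.4.5 govern is a clinical choice, and suspicion has no stated threshold.** Stopping on suspicion at any grade could end the drug after a mild reaction. The sponsor could instead write one graded rule into all three sections. But stopping on suspicion is the protocol's own rule in 7.4.5, not a new one.
- **The subset is small and not life-threatening.** It is. The defect is nevertheless a contradictory order on whether to stop or continue a drug after a possible allergic reaction, and it costs almost nothing to remove.

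**Conclusion.** The concern holds. For a suspected Grade 1 to 3 hypersensitivity reaction during an obinutuzumab infusion, Sections 5.3.4 and 7.4.5 cannot both be followed, and the protocol does not say which prevails. Followed exactly, 5.3.4 breaks a safety rule that the protocol states elsewhere, so this must be fixed.

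The conflict is confined to the 10-patient ALO cohort and does not touch any ALR result. No effect is claimed on the ALO criterion that at most 2 of 10 patients stop in the first year because of adverse events. There would be one only if stopping obinutuzumab alone counted as stopping treatment, which the protocol does not define. The conclusion rests on the text alone; the probability range is illustrative.

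**What to change.** Let Section 7.4.5 govern and leave it as written.

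1. In Section 5.3.4, delete both mentions of hypersensitivity from the interrupt and half-rate sentences, so that the rule covers IRRs only.
2. Add to both 5.3.4 and 6.6: *If the investigator suspects a hypersensitivity reaction of any grade, stop the infusion and permanently discontinue obinutuzumab (Section 7.4.5). All other infusion reactions are managed as IRRs by the grades in Section 6.6.*

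The cost is two deletions and the same two sentences added in two places. Visits, sample size and analysis are unchanged. If the sponsor prefers a graded rule for hypersensitivity, it should appear identically in 5.3.4, 6.6 and 7.4.5.
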